a. Study design, including the sequence and timing of study procedures (distinguish research procedures from those that are part of routine care).

This is a prospective, randomized, non-blinded study. The outcome variable collection will be blinded. Subjects will be randomized (1:1:1:1) within 24 hours of admission for acute decompensated heart failure to one of four treatment groups:

Treatment Protocol:

1. Intermittent bolus (every 12 hrs) furosemide diuretic therapy
2. Continuous infusion furosemide diuretic therapy
3. Intermittent bolus (every 12 hrs) furosemide diuretic therapy plus infusion of low dose intravenous dopamine (3 µg/kg/min)
4. Continuous infusion furosemide diuretic therapy plus infusion of low dose intravenous dopamine (3 µg/kg/min)

Each treatment arm protocol is detailed as follows:

1. Intermittent bolus furosemide diuretic therapy:
 - a. If the patient is not on a prior diuretic dose, a standard dose of furosemide 40mg IV every 12 hrs, with total dose of 80 mg IV over 24 hrs will be initiated.
 - b. If the patient is already on a prescribed diuretic dose, their outpatient dose will be doubled and administered as the equivalent IV dose every 12 hrs. Note: standard furosemide dosing has a 2:1 oral to IV ratio when dosing.
 - i. Example: If the prescribed home dose is furosemide 80mg by mouth twice daily, the inpatient treatment dose will be the IV equivalent of furosemide 160 by mouth twice daily (double the home dose). Therefore, the inpatient treatment dose would be furosemide 80mg IV twice daily).
2. Continuous infusion furosemide diuretic therapy
 - a. If the patient is not on a prior diuretic dose, a standard dose of furosemide 80mg IV over 24 hrs, will be initiated.
 - b. If the patient is already on a prescribed diuretic dose, their outpatient dose will be doubled and administered as the equivalent IV dose, continuously over 24 hrs. Note: standard furosemide dosing has a 2:1 oral to IV ratio when dosing.
 - i. Example: If the prescribed home dose is furosemide 80mg by mouth twice daily (160mg total per day), the inpatient treatment dose will be the IV equivalent of furosemide 320mg total per day. Therefore, the inpatient treatment dose would be furosemide 160mg IV administered continuously over 24 hrs.

3. Intermittent bolus (every 12 hrs) furosemide diuretic therapy plus infusion of low dose intravenous dopamine (3 µg/kg/min)

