 - a. Intermittent furosemide diuretic therapy from above (1.) with the addition of dopamine at 3 µg/kg/min
4. Continuous infusion furosemide diuretic therapy plus infusion of low dose intravenous dopamine (3 µg/kg/min)
 - a. Continuous furosemide diuretic therapy from above (2.) with the addition of dopamine at 3 µg/kg/min

Conversion guidelines:

2 mg oral furosemide = 1 mg intravenous furosemide

1 mg torsemide = 2 mg furosemide

1 mg bumetanide = 40 mg furosemide

Diuretic titration guidelines:

Should the patient fail to demonstrate adequate diuresis (net negative urine output of at least 500ml in 12 hrs) in response to the first treatment dose, the subsequent diuretic dose to be administered 12 hrs later (dose #2) will be doubled, or the continuous infusion will be doubled, with the goal of net negative urine output of 1 liter over 24 hrs. This titration plan can continue until adequate diuresis is achieved (at least net negative 1L urine output over 24 hr period).

Maximum Diuretic Dose:

The maximum dose permitted within study protocol will be furosemide 200 IV twice daily, or a total dose of furosemide 400 IV over 24 hrs. Should the primary team feel the patient needs higher dosing or the addition of a thiazide diuretic (or alternative agent), the patient will be considered treatment failure and will be removed from the study.

Electrolyte Repletion Guidelines:

The primary team will obtain basic metabolic panels on all study participants every 12 hours for the duration of the study. It will be the responsibility of the primary team to replete electrolytes with the goals of potassium > 4.0, and magnesium >2.0 as needed for study participants.

Fluid and Salt Restrictions:

Each study participant will be maintained on a daily 2 liter fluid and 2 gm sodium restricted diet, to be ordered by the primary team.

Treatment beyond trial end-point guidelines:

Intravenous diuretic therapy with or without dopamine according to the protocol will be continued until the treating physician decides the patient no longer requires intravenous diuretic therapy or 72 hours, whichever comes first.

All other heart failure or non-heart failure treatments will be left to the discretion of the primary team from the time of the patient's admission to the hospital and/or enrollment in the study. This includes anti-hypertensives, anti-arrhythmic drugs, and any other therapies deemed necessary for the treatment of the study subject.

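### The home-diuretic dosing rules, followed as written, give bolus and infusion patients the same starting 24-hour furosemide dose only if they take their home diuretic twice daily

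*Combined protocol and SAP*

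**What the plan says.** Section 4.a sets the starting furosemide dose for each arm. For patients already taking a diuretic, rule 1.b (intermittent bolus) reads "their outpatient dose will be doubled and administered as the equivalent IV dose every 12 hrs". Rule 2.b (continuous infusion) reads "their outpatient dose will be doubled and administered as the equivalent IV dose, continuously over 24 hrs". Both use the 2:1 oral-to-IV conversion. Arms 3 and 4 take over the furosemide rules of arms 1 and 2 and add dopamine.

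Each rule has one worked example, and both use the same patient, who takes 80 mg orally twice a day. Under 1.b, "the inpatient treatment dose will be the IV equivalent of furosemide 160 by mouth twice daily (double the home dose", which gives 80 mg IV twice daily. Under 2.b the home regimen is written as "furosemide 80mg by mouth twice daily (160mg total per day", and then "the inpatient treatment dose will be the IV equivalent of furosemide 320mg total per day", which gives 160 mg IV over 24 hours.

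For patients not on a diuretic, rule 1.a says "a standard dose of furosemide 40mg IV every 12 hrs, with total dose of 80 mg IV over 24 hrs will be initiated", and 2.a gives the same 80 mg by infusion. Rule 1.b states no 24-hour total. The maximum dose is 200 twice daily or 400 over 24 hours (no unit is printed; I take it as mg).

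The titration guideline applies one test to both schedules: "Should the patient fail to demonstrate adequate diuresis (net negative urine output of at least 500ml in 12 hrs". If the test is failed, "the subsequent diuretic dose to be administered 12 hrs later (dose #2) will be doubled, or the continuous infusion will be doubled".

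**The concern.** Rule 1.b gives a doubled dose every 12 hours and does not say that a daily total is divided. Rule 2.b gives a doubled dose once per 24 hours. The 1.b example works per administration and the 2.b example works on the daily total. These agree when the patient takes two home doses a day, and only then. No example or instruction covers any other home frequency.

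Intermittent versus continuous diuresis is a stated objective (Section 2) and one of the two factors in the factorial design (Section 7). To the extent that staff follow the wording for patients not on twice-daily dosing, the comparison of arms 1+3 with arms 2+4 mixes dose with mode of administration. Analysis by intention to treat does not remove that. The most direct route is secondary endpoint 8, which records whether the IV diuretic dose had to be raised: patients with the same home regimen would reach the same 12-hour urine-output test having received different amounts of drug.

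**Working it through.** **Inputs.** Rules 1.b and 2.b with their examples, the 2:1 oral-to-IV conversion, and the maximum of 400 mg IV per 24 hours, all from Section 4.a. Let D be the oral furosemide-equivalent per home administration (mg) and f the number of administrations per day.

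**Formulas, below the cap.**
- Bolus, 1.b as written (per administration, as in its example): each dose is 2D/2 = D mg IV, given twice, so 2D per 24 hours.
- Infusion, 2.b (daily total, as in its example): 2Df/2 = Df per 24 hours.
- Ratio of bolus to infusion: 2D/(Df) = 2/f.
- Bolus if the doubled daily total is split in two: 2 × (Df/2) = Df, so the ratio is 1.0 at every f.

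**Reproducing the plan's examples.** With D = 80 and f = 2, 1.b gives 80 mg IV twice daily = 160 mg per 24 hours, and 2.b gives 80 × 2 = 160 mg. Both match. The split reading also gives 160 mg, so the examples cannot tell the two readings apart. They do rule out a third reading, in which the whole doubled daily total is given every 12 hours: that would be 160 mg twice daily = 320 mg, not the stated 160 mg.

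**Other home frequencies (mg IV per 24 hours).**

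| Home oral dose | Bolus, 1.b as written | Infusion, 2.b | Ratio | Bolus, daily total split |
|---|---|---|---|---|
| 40 once daily | 80 | 40 | 2.0 | 40 |
| 80 once daily | 160 | 80 | 2.0 | 80 |
| 200 once daily | 400 | 200 | 2.0 | 200 |
| 80 twice daily | 160 | 160 | 1.0 | 160 |
| 40 three times daily | 80 | 120 | 0.67 | 120 |
| 80 three times daily | 160 | 240 | 0.67 | 240 |

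The once-daily ratio of 2.0 holds up to D = 200, where the bolus total 2D reaches 400. The three-times-daily ratio of 0.67 holds while 3D is at most 400, that is, D up to about 133. Beyond these points the result depends on whether a starting dose is truncated at the cap, which the Maximum Diuretic Dose paragraph does not say. If it is truncated, 300 mg once daily gives 400 v 300 (1.33) and 400 mg once daily gives 400 v 400 (1.0).

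**What titration does, home dose 80 mg once daily.** By the 12-hour check the bolus patient has received 80 mg and the infusion patient 80 × 12/24 = 40 mg. Dose received in the first 24 hours:

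| Doubled at 12 hours | Bolus | Infusion | Ratio |
|---|---|---|---|
| Neither | 80 + 80 = 160 | 40 + 40 = 80 | 2.0 |
| Both | 80 + 160 = 240 | 40 + 80 = 120 | 2.0 |
| Infusion only | 80 + 80 = 160 | 40 + 80 = 120 | 1.33 |
| Bolus only | 80 + 160 = 240 | 40 + 40 = 80 | 3.0 |

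The daily rates become equal at that check only in the third row, and the doubling there is itself an endpoint 8 event in the infusion arm. For 40 mg three times daily the gap runs the other way: 40 mg by bolus against 120 × 12/24 = 60 mg by infusion at 12 hours.

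**The case against.** The best reply is that the text as a whole points to equal daily totals. The two examples both come to 160 mg, the diuretic-naive starts are both 80 mg, and the maximum doses match. The examples are part of the rules, and the 1.b example describes its result as twice the home dose. Read as written, 80 mg once daily becomes 160 mg IV by bolus, equivalent to 320 mg orally, which is four times the home daily dose and at odds with that description. Both schedules are then titrated to the same target, crossover is allowed, and nothing in the documents shows that staff would dose literally.

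Most of this stands. It makes the problem a gap in the wording, not a chosen inequality. But inferring the intent is not the same as having an instruction, and both examples use the one frequency at which the mismatch cannot show. Nor would the literal dose always look odd at the bedside: 40 mg once daily becomes 40 mg IV every 12 hours, the same as the diuretic-naive bolus start, whereas the split reading gives 20 mg every 12 hours, half of it. Titration need not close the gap either.

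A reader might infer that the bolus arms will receive more furosemide overall, or that an average dose ratio for the trial can be worked out, or that the primary creatinine endpoint is biased. The documents support none of these. They give neither the mix of home dosing frequencies nor how staff would read 1.b, and once-daily and three-times-daily users pull in opposite directions.

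**Conclusion.** The concern holds as a defect in the written dosing rules. With 1.b taken per administration and 2.b on the daily total, as their examples do, starting 24-hour doses match only for twice-daily home users. The bolus-to-infusion ratio is 2.0 for once-daily users at up to 200 mg oral furosemide equivalent and 0.67 for three-times-daily users below the cap. It is 1.0 for everyone if staff split the daily total, which is probably what was meant.

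The effect on arms 1+3 v 2+4, including endpoint 8, cannot be sized or signed from the documents, and it may be nil. Diuretic-naive and twice-daily patients are not affected. Nor is the dopamine comparison, on which the sample size is built, because each side of it pools both schedules. These are starting doses; response-based titration and discretionary crossover mean that they do not fix the dose delivered over 72 hours.

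**What to change.** In both 1.b and 2.b, state that the total daily home dose, in furosemide equivalents, is doubled and converted to IV, and that this 24-hour total is given as two equal doses 12 hours apart (arms 1 and 3) or infused over 24 hours (arms 2 and 4). Add a once-daily example to each rule: 80 mg once daily becomes 40 mg IV every 12 hours, or 80 mg IV over 24 hours. The existing twice-daily examples remain correct.

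The cost is one sentence and one example per rule. No extra patients, procedures or data are needed, since home medications are already recorded at baseline.

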After 72 hrs, the study drug will be discontinued, a primary assessment will be made of primary and secondary endpoints, and all further treatment is at the treating physician's discretion.

Note: Study participants will be permitted to cross over into non-assigned arms of the study, however the study analysis will be completed as an intention-to-treat study. It will be left to the discretion of the primary team, with supervision from the study investigators as to whether a cross over is necessary within the 72 hr study time frame.

Baseline Assessments and Data to be Recorded (all are standard of care unless indicated by *)

1. Directed history and physical exam, focused on signs and symptoms of congestion/volume overload
2. Vital signs (HR, BP, O2 saturation, weight, height)
3. Home medications
4. Basic metabolic panel including serum creatinine, BUN, electrolytes and magnesium
5. Serum Pro-BNP level
6. Serum Cystatin C*
7. High-sensitivity troponin
8. Baseline electrocardiogram
9. Transthoracic echocardiogram if one has not been obtained within 1 year prior to admission
 - i. Including left ventricular (LV) ejection fraction, LV dimensions, left atrium size (LA), LV mass, right ventricular function parameters (RVSP), valvular assessment
10. 6 min walk test*
11. Patient Global Well being assessment by VAS*
12. Dyspnea assessment by VAS*
13. Frailty Index*
14. Blood sample for biomarkers and genetic testing for heart failure*
15. Urine sample for biomarkers*

24 hr Assessment:

1. Routine vitals assessment with weight recording
2. I/O assessment – to be recorded and totaled for each 12 period
3. Twice daily basic metabolic panel and serum magnesium

72 hr Assessment and Data to be Recorded:

1. Routine vitals assessment with weight recording
2. I/O assessment – to be recorded and totaled for each 24 period
3. Twice daily basic metabolic panel and serum magnesium
4. Serum Pro-BNP level*
5. Serum Cystatin C*
6. High-sensitivity troponin
7. 6 min walk test*
8. Patient Global Well being assessment by VAS*
9. Dyspnea assessment by VAS*
10. Frailty Index*
11. Changes in cardiovascular medications
12. Assessment for serious cardiovascular events

At Discharge Assessment and Data to be recorded:

1. Routine vitals assessment with discharge weight recording
2. I/O assessment – to be recorded and totaled for each 24 period
3. Basic metabolic panel including creatinine, BUN
4. Serum Pro-BNP level
5. Serum Cystatin C*
6. High-sensitivity troponin
7. 6 min walk test*

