8. Patient Global Well being assessment by VAS*
9. Dyspnea assessment by VAS*
10. Frailty Index*
11. Changes in cardiovascular medications
12. Assessment for serious cardiovascular events
13. Urine and serum samples for biomarkers*

*Investigational data to be collected as part of trial protocol.

Day 30, 6 month, and 1 year Assessment and Data to be Recorded:

Patient charts will be reviewed and patients will receive a phone call to assess for potential re-hospitalizations and major adverse cardiovascular events at each respective endpoint since discharge. The first readmission event following index hospitalization will be adjudicated by a Clinical Event Committee consisting of 2-3 cardiologists not directly in contact with patients enrolled in the study.

Vascular Access:

All patients in the intermittent bolus diuretic strategy arm will require the placement of two functioning peripheral IV catheter. Patients assigned to the continuous diuretic strategy and either treatment arm that requires low-dose dopamine will need at least 2 peripheral IVs suitable for continuous infusions. Central venous catheter placement may be required should it be difficult to obtain or maintain peripheral IV

access. This would be determined by the primary team, with consent obtained separately for this procedure by the primary team.

Foley Catheter Placement:

All patients enrolled in this trial will be encouraged to have a foley urinary catheter placed. This will allow for improved patient tolerance of diuresis and improved accuracy of I/O assessment by nursing staff. This will not be required, however, for enrollment in the trial.

b. Study duration and number of study visits required of research participants.

The study duration is the hospital admission. The study drugs will be mandated for 72 hours following enrollment. There are no outpatient visits but patients will receive follow up phone calls, at 30 days and at 6 months following discharge.

c. Blinding, including justification for blinding or not blinding the trial, if applicable.

The treatment is not blinded. The primary endpoint of change in renal function will be objectively obtained and should not be affected by lack of blinding. All other variables will be obtained by an investigator blinded to the study drug assignment.

d. Justification of why participants will not receive routine care or will have current therapy stopped.

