Participants will receive routine care for their acute decompensated heart failure. Currently, many practitioners utilize both intermittent and continuous furosemide infusions in this patient group. Low dose, or renal-dose dopamine is also a frequent adjunct to diuretics to aid in diuresis.

e. Justification for inclusion of a placebo or non-treatment group.

There is no placebo group.

f. Definition of treatment failure or participant removal criteria.

Subjects will be removed from the protocol for:

1. The development of hemodynamic instability including hypotension (SBP < 90), hypertensive emergency, or unstable arrhythmias (SVT or VT).
2. The development of pulmonary edema requiring inotropes or vasopressor or more than 50% inspired oxygen.
3. The development of acute coronary syndrome.
4. The development of acute kidney injury by KDIGO criteria as follows¹:
 - a. If the patient develops Stage II AKI (by KDIGO criteria), the study treatment will be held and a clinical decision will be made whether to resume or discontinue treatment drug
 - b. If the patient develops Stage III AKI (by KDIGO criteria), the study treatment will be discontinued and the patient will be classified as treatment failure and followed only for outcome recording.
5. The need for renal replacement therapy
6. New atrial fibrillation or other supraventricular tachyarrhythmia
7. Sustained ventricular arrhythmias

8. Requirement of furosemide dose increase beyond the study maximum of 200 IV twice daily (or 400 IV over 24 hrs), or the need for addition of thiazide diuretic.

g. Description of what happens to participants receiving therapy when study ends or if a participant's participation in the study ends prematurely.

Once the study period ends, or if the study ends prematurely, the patient will receive standard heart failure management at the discretion of the primary team. The patient will resume standard outpatient follow up as advised by the primary team at the time of discharge.

5. Inclusion/Exclusion Criteria

a. Inclusion Criteria :

1. Admission to the hospital for acute decompensated heart failure within 24 hours of enrollment into the study.
 - a. Diagnosis of heart failure as defined by the presence of at least 1 symptom (dyspnea, orthopnea, or edema) AND 1 sign (rales on auscultation, elevated jugular venous pulse, hepatojugular reflex, peripheral edema, ascites, pulmonary vascular congestion on chest radiography)
2. Patient ≥ 18 years of age

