14. 30 day, 6 month, and 1 year hospital readmission or ER visit for major adverse cardiovascular event, heart failure, renal failure (development of CKD, ESRD, or dialysis need by KDIGO criteria), syncope, or arrhythmia. Readmission events will be adjudicated by a Clinical Event Committee consisting of 2-3 cardiologists not directly in contact with patients enrolled in the study.

KDIGO AKI Definition¹:

AKI is defined by any of the following 3 criteria:

1. Increase in serum creatinine by ≥ 0.3 mg/dl (≥ 26.5 $\mu\text{mol/l}$) within 48 hours; OR
2. Increase in serum creatinine to ≥ 1.5 times baseline, which is known or presumed to have occurred within prior 7 days; OR
3. Urine volume < 0.5 ml/kg/h for 6 hours

Stages of AKI as defined by KDIGO Criteria are as follows:

Stage	Serum Creatinine	Urine Output
1	1.5-1.9 times baseline OR ≥ 0.3 mg/dl (≥ 26.5 $\mu\text{mol/l}$) increase	< 0.5 ml/kg/h for 6-12 hours
2	2.0-2.9 times baseline	< 0.5 ml/kg/h for ≥ 12 hours
3	3.0 times baseline OR increase in serum creatinine to ≥ 4.0 mg/dl (≥ 353.6 $\mu\text{mol/l}$) OR initiation of renal replacement therapy OR, in patients < 18 years, decrease in eGFR to < 35 ml/min per 1.73 m ²	< 0.3 ml/kg/h for ≥ 24 hours OR Anuria for ≥ 12 hours

a. Statistical plan including sample size justification and interim data analysis.

1. Overview:

- a. This is a factorial design study evaluating two simultaneous unrelated interventions. Sample size justification and primary endpoint analysis is described below.

2. Analysis of Primary Endpoints:

- a. The primary analysis will be conducted on an intention-to-treat basis. Non-parametric testing for the continuous primary endpoint (creatinine) will be performed using the Wilcoxon-Mann-Whitney U test. Confirmatory test for interaction between dopamine and diuretic strategy will be performed with linear regression analysis with dopamine*diuretic term, $p=0.10$ for significance.

3. Sample Size Justification:

- a. A difference of 30% in creatinine pre and post- treatment is considered to be clinically meaningful. Setting parameters as follows: two-sided, alpha (Type I error rate) of 0.05, power of 0.80, and using mean creatinine calculations based on our own retrospective experience at

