The investigators will report all adverse events to the IRB and will follow these patients throughout the duration of the study.

8. Risks

a. Medical risks, listing all procedures, their major and minor risks and expected frequency.

Furosemide is considered a standard of care diuretic for the treatment of acute heart failure. While it is a commonly used medication, the risks commonly associated with furosemide include (but are not limited to) acute kidney injury (pre-renal azotemia, acute interstitial nephritis), and electrolyte disturbances (hypokalemia, hypomagnesemia). Severe but uncommon risks of furosemide include orthostatic hypotension, drug hypersensitivity syndrome, erythema multiforme, erythroderma, Stevens-Johnson syndrome, toxic epidermal necrolysis, pancreatitis, arnucytosis, aplastic anemia, thrombocytopenia, anaphylactoid reaction, and anaphylaxis.

Diminished hearing or deafness, reversible and irreversible, has been reported with the use of furosemide. Usually, the effects on hearing are associated with fast injections, severe renal impairment (loss of kidney function), hypoproteinemia (low protein in the blood), use of higher than recommended doses or in combination with other ototoxic agents. The effects on hearing are rare and would more likely occur from intermittent doses, than continuous infusions.

Dopamine is often used in the treatment of acute heart failure exacerbation to assist with diuresis, particularly when there is a risk of development of acute kidney injury. The common side effects and risks associated with low-dose dopamine include chest pain, increase in blood pressure, fast or irregular heart rates, injection site reaction, and hair follicles may stand erected. Serious but uncommon risks include ectopic beats, ventricular arrhythmia, wide QRS complex, and gangrenous disorder.

b. Steps taken to minimize the risks.

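### Removal of rescued patients is worded ambiguously and, read literally, can take out of the intention-to-treat analysis the 72-hour creatinine it needs

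*Combined protocol and SAP*

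**What the plan says.** **Removal.** Under Maximum Diuretic Dose (Section 4.a), a patient who the team feels needs a higher dose or "the addition of a thiazide diuretic (or alternative agent), the patient will be considered treatment failure and will be removed from the study". Section 4.f opens its eight numbered criteria with "Subjects will be removed from the protocol for". The Early stopping rules in Section 7 repeat the criteria as grounds for leaving the trial. The same rescue event is therefore an exit from the study, from the protocol or from the trial, depending on the section.

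**Follow-up after removal.** For Stage III AKI (Section 4.f, item 4b, repeated in Section 7), "the study treatment will be discontinued and the patient will be classified as treatment failure and followed only for outcome recording". For Stage II AKI, treatment is held and a clinical decision follows. After the Section 7 list comes: "The investigators will report all adverse events to the IRB and will follow these patients throughout the duration of the study". Section 4.b defines that duration: "The study duration is the hospital admission". Section 4.g, on early termination, speaks only of care: "if the study ends prematurely, the patient will receive standard heart failure management at the discretion of the primary team". Section 8.b ends the dopamine infusion for persistent or recurrent tachycardia and labels this a treatment failure, without mentioning follow-up.

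**Analysis.** The primary endpoint is percent change in creatinine between randomization and 72 hours. Section 7 states: "The primary analysis will be conducted on an intention-to-treat basis". The crossover note in Section 4.a says that crossovers are allowed, "however the study analysis will be completed as an intention-to-treat study". No method is given for a missing 72-hour value.

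**The concern.** An intention-to-treat comparison needs the 72-hour creatinine of every randomized patient, including those who stop the assigned treatment. A site that takes removal from the study at its word may stop collecting data at rescue.

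That loss would not be random. Rescue depends on response to the assigned strategy and on the judgement of a team that knows the assignment (Section 4.c). It may also differ by arm. Section 4.d describes low-dose dopamine as an aid to diuresis, so diuretic rescue could be commoner without it. Section 8.a lists fast or irregular heart rates and ventricular arrhythmia as dopamine risks, and arrhythmias appear in removal items 1, 6 and 7. Different kinds of patient could leave different arms. Even equal removal counts would then not protect a Wilcoxon test restricted to those who stayed. Blinded outcome collection does not help, because the treating team decides on removal.

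**Working it through.** **1. The plan's own figure on loss.** Section 7 needs 63 per pooled arm and enrols 140. So 2 × 63 = 126, and 126/140 = 0.90, which implies a 10% allowance. The plan states neither that rate nor whether removed patients count as drop-outs. The allowance protects the count; it does nothing about selective loss.

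**2. Which removal items in Section 4.f carry outcome recording.**
- Explicit: item 4b (Stage III AKI).
- Covered through the definition: item 5 (renal replacement therapy), because starting it is KDIGO Stage 3.
- Hold and decide, with no follow-up clause: item 4a (Stage II AKI).
- No clause: items 1, 2, 3, 6, 7 and 8 (instability, pulmonary edema, acute coronary syndrome, new supraventricular arrhythmia, sustained ventricular arrhythmia, diuretic rescue). That is six of the eight.

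**3. Can removal come before 72 h?** Inputs from Section 4.a: the ceiling is 200 mg IV per dose twice daily, or 400 mg/24 h by infusion. The standard start is 40 mg every 12 h or 80 mg/24 h. The home-dose example starts at 80 mg IV twice daily or 160 mg/24 h. The dose is doubled after an inadequate response. The first step is at 12 h; the interval for later steps can be read as 12 h or 24 h. For a persistent non-responder doubled at every step:
- 12-hourly, standard start: 40 (0 h), 80 (12 h), 160 (24 h), 320 > 200 (36 h).
- 12-hourly, home-dose example: 80 (0 h), 160 (12 h), 320 > 200 (24 h).
- 24-hourly after dose 2, standard start: 40 (0 h), 80 (12 h), 160 (36 h), 320 > 200 (60 h).
- 24-hourly after dose 2, home-dose example: 80 (0 h), 160 (12 h), 320 > 200 (36 h).

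The infusions pass 400 mg/24 h, at 640, at the same times.

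| Start | 12-hourly (gap to 72 h) | 24-hourly after dose 2 (gap to 72 h) | One step held at the ceiling first: 12-hourly; 24-hourly |
|---|---|---|---|
| Standard | 36 h (36 h) | 60 h (12 h) | 48 h; 84 h |
| Home-dose example | 24 h (48 h) | 36 h (36 h) | 36 h; 60 h |

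Seven of the eight times fall before the endpoint; 84 h falls after it. A thiazide or alternative agent can be added below the ceiling, so removal can also come earlier.

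**4. Size of a possible bias (illustration on assumed values).** Let a share p of an arm be removed, and let their creatinine change be m points worse than that of completers. The full-arm mean is then the completers' mean plus p × m. With the same m in both arms, a completers-only difference is off by (p₂ − p₁) × m. The documents give neither p nor m. For m = 30 to 60 points:
- 5% v 10%: 0.05 × m = 1.5 to 3 points
- 5% v 15%: 0.10 × m = 3 to 6 points
- 5% v 20%: 0.15 × m = 4.5 to 9 points
- 10% v 10%: 0 points, provided m is the same in both arms

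The plan calls a 30% difference clinically meaningful. These figures are for means, whereas the primary test uses ranks, so they show the mechanism rather than predict a result.

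**The case against.** The texts can be reconciled. Exit from the protocol in Section 4.f can mean exit from protocol treatment. The follow-up sentence in Section 7 comes straight after the list of removed subjects, who are the natural meaning of these patients, and the admission covers 72 h for anyone still in hospital. With intention-to-treat stated twice, the coherent reading is to stop treatment, keep following and analyse as randomized. Panels are drawn every 12 h on study participants, and Section 8.b calls twice-daily panels standard care, so the chart value will often exist. Crossover within 72 h gives a poor responder an option short of removal.

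Much of this stands. A reader might infer that the protocol flatly contradicts itself; it does not, because this reading is available. A reader might also see the tachycardia label in Section 8.b as a further, conflicting disposition of treatment failures, but it is a recording label and says nothing about data. Nor is the silence of Section 4.g evidence that collection stops, since its heading asks about care.

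The objection does not close the gap. The follow-up sentence is joined to adverse-event reporting and names neither outcomes nor the creatinine. If it already secured outcome recording for everyone removed, the Stage III AKI clause would be unnecessary. The panel rule does not say whether a removed patient is still a participant. A chart value helps only if the plan says that it is collected and analysed.

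**Conclusion.** The concern holds as an ambiguity that should be resolved. One reading keeps the intention-to-treat analysis intact. The literal reading removes patients for reasons tied to response and possibly to arm, and turns the primary comparison into one of completers. The plan does not say which applies.

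It would be tempting to conclude that 72-hour values will be lost, or that non-responders will typically leave at 24 to 36 h. The documents support neither. The times assume a persistent non-responder doubled at every step, while the actual trigger is what the team feels is needed. They show only that removal before 72 h is possible. The number affected cannot be derived, and the bias figures rest wholly on assumed removal rates and creatinine differences.

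**What to change.** - In Section 4.a (Maximum Diuretic Dose), Section 4.f and the Early stopping rules of Section 7, replace removal from the study, protocol or trial with discontinuation of study treatment and continued follow-up for outcome recording, as item 4b already does. Keep the Stage II AKI hold-and-decide rule.
- Apply the same follow-up wording to the dopamine tachycardia failure in Section 8.b.
- Record the reason and time of discontinuation and any rescue agent.
- Take the 72-hour creatinine from the routine 12-hourly panels and analyse it in the assigned arm.
- If there is no 72-hour value, for example after discharge before 72 h, use the last available in-hospital creatinine in the primary analysis. Add a sensitivity analysis that ranks treatment failures without a 72-hour value as worst outcomes, which fits the rank test already planned.

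The cost is the wording changes, one case-report entry and one added sensitivity analysis. While the patient is in hospital no extra blood draw is needed, and clinicians remain free to rescue. The last-available rule assumes little change between that sample and 72 h; the sensitivity analysis tests this only for treatment failures.
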